1.3.3 Schedule of assessments

The schedule of procedures and assessments during the study is summarised in [Table 2](#).

SAP Final: Version 6.0: 17 August 2023

Table 2 Study Procedures and Assessments

| Assessment | Pre-treatment Period | Treatment Period | | | | | | Post-treatment Follow-up Period ^d |
|--|----------------------------------|-------------------------|------------------------|------------------------|---------------------------------|--|--|--|
| | Screening | Baseline ^a | Week 2 | Week 4 | Week 8 | Every 4 weeks | End of Study Treatment Visit ^b or Early Study Withdrawal Visit ^c | Follow-Up |
| Visit 1 | Visit 2 | Visit 3 | Visit 4 | Visit 5 | Visit 6 to Visit X | 30 days after the last dose of treatment | Every 12 weeks | |
| Before first cabozantinib intake | Day 1 | Day 15 (± 2 Days) | Day 29 (± 2 Days) | Day 57 (± 2 Days) | Day 85 to Day X (± 5 Days) | (+15 Days) | (± 15 Days) | |
| Informed consent form | X ^e | | | | | | | |
| Eligibility Criteria | X | X | | | | | | |
| Demography | X | | | | | | | |
| Medical history | X | | | | | | | |
| RCC history | X | | | | | | | |
| Prior surgery/radiotherapy/chemotherapy/medications related to RCC | X | | | | | | | |
| Smoking habits/status | X | | | | | | | |
| Physical examination | ≤ 15 Days prior to baseline | X (prior to first dose) | X | X | X | Every 4 weeks | X | |
| Weight | ≤ 15 Days prior to baseline | X (prior to first dose) | X | X | X | Every 4 weeks | X | |
| Vital signs | ≤ 15 Days prior to baseline | X (prior to first dose) | X | X | X | Every 4 weeks | X | |
| ECOG performance status | ≤ 15 Days prior to baseline | X (prior to first dose) | X | X | X | Every 4 weeks | X | |

CONFIDENTIAL

SAP Final: Version 6.0: 17 August 2023

| | Pre-treatment Period | Treatment Period | | | | | | Post-treatment Follow-up Period ^d |
|---|----------------------------------|--|--|---------------------|---------------------|------------------------------|--|---|
| Assessment | Screening | Baseline ^a | Week 2 | Week 4 | Week 8 | Every 4 weeks | End of Study Treatment Visit ^b or Early Study Withdrawal Visit ^c | Follow-Up |
| | Visit 1 | Visit 2 | Visit 3 | Visit 4 | Visit 5 | Visit 6 to Visit X | 30 days after the last dose of treatment | Every 12 weeks |
| | Before first cabozantinib intake | Day 1 | Day 15 (±2 Days) | Day 29 (±2 Days) | Day 57 (±2 Days) | Day 85 to Day X (±5 Days) | (+15 Days) | (±15 Days) |
| 12-lead ECG | ≤15 Days prior to baseline | X (prior to first dose) ^f | | X | | Every 12 weeks | X | |
| Haematology and blood biochemistry | ≤15 Days prior to baseline | X (prior to first dose) ^f | X | X | X | Every 4 weeks | X | |
| Coagulation assessments | ≤15 Days prior to baseline | X (prior to first dose) ^f | X | X | X | Every 4 weeks | | |
| Urinalysis, microscopic urine examination and urine chemistry (including UPCR) ^g | ≤15 Days prior to baseline | X (prior to first dose) ^f | X | X | X | Every 4 weeks | X | |
| Pregnancy test (female subjects only, if applicable) | ≤7 days prior to baseline | X (prior to first dose) ^f | Urinary and/or pregnancy blood tests are mandatory at every visit | | | | X | |
| Thyroid function test (FT4, TSH) | ≤15 days prior to baseline | X (prior to first dose) ^f | Every 4 weeks | | | | X | |
| Chest/Abdomen/Pelvis (C/A/P) CT/MRI | ≤28 days prior to baseline | X ^f | Every 12 weeks (±10 days) while on protocol treatment beginning at Week 12 (i.e. Week 12, Week 24, Week 36, etc) until the end of study and additionally if clinically indicated | | | | | X ^h |
| Brain CT/MRI and Bone scintigraphy Scan (only if indicative of metastases) | ≤28 days prior to baseline | Only if indicative of brain and/or bone metastases at screening or if signs or symptoms suggestive of metastases develop | | | | | | X ^h (only if indicative of metastases) |

CONFIDENTIAL

SAP Final: Version 6.0: 17 August 2023

| | Pre-treatment Period | Treatment Period | | | | | | Post-treatment Follow-up Period ^d |
|--|-----------------------------------|---|---|------------------------|------------------------|---------------------------------|--|--|
| Assessment | Screening | Baseline ^a | Week 2 | Week 4 | Week 8 | Every 4 weeks | End of Study Treatment Visit ^b or Early Study Withdrawal Visit ^c | Follow-Up |
| | Visit 1 | Visit 2 | Visit 3 | Visit 4 | Visit 5 | Visit 6 to Visit X | 30 days after the last dose of treatment | Every 12 weeks |
| | Before first cabozantinib intake | Day 1 | Day 15 (± 2 Days) | Day 29 (± 2 Days) | Day 57 (± 2 Days) | Day 85 to Day X (± 5 Days) | (+15 Days) | (± 15 Days) |
| Cabozantinib intake ⁱ | | All subjects will be treated with oral cabozantinib 60 mg once daily (q.d.). In case of treatment-emergent toxicity, the Investigator may decide to reduce the dose to 40 mg or 20 mg | | | | | | |
| Dispense/return of oral study drug and compliance accounting | | X | | X | X | X | X | |
| AEs ^{j,k} | ≤ 15 Days prior to Screening | X | X | X | X | X | X | X ^k |
| Prior and concomitant therapies ^l | ≤ 30 Days prior to baseline | X ^l | X ^l | X ^l | X ^l | X ^l | X ^l | |
| Other cancer treatment | | | | | | | | X |
| Survival status | | | | | | | | X |
| HRQOL (FKSI-DRS) ^m | | X (prior to first dose) | Every 12 weeks while on protocol treatment beginning at Week 12 (i.e. Week 12, Week 24, Week 36, etc) until the End of Study Treatment visit or Early Study Withdrawal visit. | | | | | |

Abbreviations: AEs = Adverse events; CT = Contrast tomography; ECG = Electrocardiogram; ECOG = Eastern Cooperative Oncology Group; eCRF = Electronic case report form; FKSI-DRS = Functional Assessment of Cancer Therapy–Kidney Symptom Index–Disease-Related Symptoms; FT4 = Free thyroxine 4; HRQOL = Health-related quality of life; MRI = Magnetic Resonance Imaging; RCC = Renal cell carcinoma; SAE = Serious adverse event; TSH = Thyroid-stimulating hormone

^a Screening and baseline visits can take place the same day as long as all eligibility criteria/parameters are available and checked prior to the first dose of cabozantinib.

^b This visit will be held for subjects who have discontinued study treatment whatever the reason (e.g. disease progression or unacceptable toxicity).

^c All included subjects who prematurely stopped the study due to withdrawal of consent during study treatment period will attend the Early Study Withdrawal visit.

^d During the Post-treatment Follow-up period, subjects will be contacted every 12 weeks (± 15 days) starting after the End of Study Treatment visit to assess survival status and document receipt of subsequent anti-cancer therapy. These assessments will be continued until the subject expires or the end of the study (18 months after the last subject included in the study received the first cabozantinib dose), whichever occurs first.

CONFIDENTIAL

SAP Final: Version 6.0: 17 August 2023

^e Informed consent must be provided before any study-specific procedures are performed; however, evaluations performed as part of routine care prior to informed consent can be used as Screening evaluations if permitted by the Institutional Review Board (IRB)/Ethics Committee (EC) policies of the investigational site.

^f These assessments are intended to confirm suitability for treatment after the Screening visit. There is no need to perform them again at baseline, unless the subject's clinical status has changed (e.g. onset of new symptoms indicative of clinical deterioration). If these assessments are performed at screening and baseline visits, results must be available to be reviewed by the Investigator prior to first dose.

^g Microscopic urine examination to be performed at baseline and after that only at the discretion of the Investigator (results are not to be collected in the eCRF except in case of clinically abnormal findings, which are to be reported as an AE). Urine chemistry (24-hour urine protein tests or urine protein/creatinine ratio [UPCR]) may be performed at any scheduled or unscheduled visit at the discretion of the Investigator and based on results of routine urinalysis or as clinically indicated.

^h Follow-up for radiographic progression, tumour assessment should be performed until radiographic progression confirmed by the Investigator only for subjects who have discontinued cabozantinib treatment before radiographic disease progression and who have not withdrawn consent.

ⁱ Cabozantinib will be self-administered at home until study treatment is discontinued.

^j Information on new or worsening AEs will be collected from date of the signed informed consent until the end of study treatment, at each study visit, by telephone call or by spontaneous report by the subject. Any AEs and SAEs that are ongoing 30 days after the date of the last cabozantinib dose are to be followed until resolution or until the Investigator considers the event is stable or irreversible.

^k During the follow-up period, any SAEs that occur more than 30 days after the date of the last cabozantinib dose, assessed as related to study treatment or study procedures will also be collected and followed until resolution or stability according to the Investigator.

^l Information on prior and concomitant medication will be collected up to 30 days before baseline until 30 days after the date of the last cabozantinib dose.

^m The FACIT and all related works are owned and copyrighted by, and the intellectual property of [name]. Permission for use of the FKSI-DRS questionnaire is obtained by contacting [name] at [contact].

CONFIDENTIAL

SAP Final: Version 6.0: 17 August 2023

1.3.4 *Planned sample size*

For cohort A, the hypothesis for sample size computation is that cabozantinib will demonstrate a clinically significant increase in the response rate as compared to historical control in 2nd line treatment. A therapy will be considered clinically meaningful if it provides a significant benefit in ORR as assessed by independent central review over a standard rate of 10% (conservative threshold in reference to the response rate of everolimus in the METEOR study [1, 2], exact 95% CI: 1.7-5.9). Assuming approximately 7% non-evaluable subjects (i.e. subjects who received at least one dose of study medication but did not provide a baseline for the tumour according to RECIST 1.1), 74 subjects in cohort A provides at least 80% power (at one-sided significance level (alpha) of 0.025) to reject the null hypothesis of 10% ORR in favour of an alternative hypothesis of 23% ORR.

For cohort B, no formal sample size determination was performed as the enrolment will stop when the recruitment in cohort A will be reached. We anticipate approximately 40 subjects recruited in cohort B.

2 SUBJECT POPULATIONS (ANALYSIS SETS)

The Screened population is all subjects screened (i.e. who signed the informed consent).

The Included population is all screened subjects who fulfilled the inclusion and exclusion criteria. In case a subject did not fulfil the inclusion and exclusion criteria but received at least one dose of study medication, this subject will be considered as part of the included population.

2.1 **Efficacy**

2.1.1 *Efficacy population - IRC*

The Efficacy population - IRC is all included subjects who received at least one dose of study medication and provided a Baseline assessment for the tumour according to RECIST 1.1, i.e. reporting at least one target lesion at baseline based on IRC assessment.

2.1.2 *Efficacy population - investigator*

The Efficacy population – investigator is all included subjects who received at least one dose of study medication and provided a Baseline assessment for the tumour according to RECIST 1.1, i.e. reporting at least one target lesion at baseline based on investigator assessment.

2.1.3 *Per Protocol (PP) population - IRC*

The Per Protocol population - IRC is all subjects in the efficacy population – IRC who have no impacting major protocol deviations (i.e. that could potentially affect the primary efficacy endpoint outcome for the subject).

Criteria for exclusion from the Per Protocol population will be provided in the Protocol Deviation Specifications. Listings of subjects regarding inclusion in each population and satisfying the population definition and associated data will be reviewed by the study team.

SAP Final: Version 6.0: 17 August 2023

Reasons for exclusion from Per Protocol population will be presented in a summary table by cohort.

2.1.4 *Per Protocol (PP) population - investigator*

The Per Protocol population – investigator is all subjects in the efficacy population – investigator who have no impacting major protocol deviations (i.e. that could potentially affect the primary efficacy endpoint outcome for the subject).

Criteria for exclusion from the Per Protocol population will be provided in the Protocol Deviation Specifications. Listings of subjects regarding inclusion in each population and satisfying the population definition and associated data will be reviewed by the study team.

Reasons for exclusion from Per Protocol population will be presented in a summary table by cohort.

2.2 *Safety*

The safety population is all included subjects who received at least one dose of study medication.

2.3 *Primary population*

In the rest of the SAP, we used the generic name efficacy population and PP population but it is implicit that efficacy population - investigator and PP population - investigator will be applicable for all analyses based on investigator assessment and efficacy population - IRC and PP population - IRC for all analyses based in IRC assessment.

Analysis based on the primary efficacy endpoint will be performed on the efficacy population in cohort A. Analyses based on the secondary efficacy endpoints will be performed on the efficacy population in each cohort separately. In addition, ORR and PFS according to local Investigator's review per RECIST 1.1 as well as OS will be presented in the overall population (cohort A + cohort B).

Sensitivity efficacy analyses will be based on PP population. Efficacy analyses in the PP population will be presented if there is a difference greater than 15% between efficacy population and PP population. The difference will be checked for each cohort separately. In case the difference is greater than 15% for one cohort only, only this cohort will be presented in both efficacy population and PP population.

The analyses of safety data will be performed based on the safety population in each cohort separately and overall.

3 STATISTICAL METHODS

3.1 *Statistical analysis strategy*

The statistical analyses will be performed in accordance with International Conference on Harmonisation (ICH) E9 guideline and will be based on the pooled data from the individual study sites for each cohort separately, unless otherwise stated.

Statistical analyses will be performed by Parexel, managed by the Sponsor's biometry department.

3.1.1 *Primary efficacy endpoint*

The primary efficacy endpoint is:

SAP Final: Version 6.0: 17 August 2023

- ORR defined as the proportion of subjects with a best overall response (BOR) of a partial response (PR) or complete response (CR) at any timepoint as determined by independent central review per Response Evaluation Criteria in Solid Tumours (RECIST 1.1) in cohort A.

Details regarding the independent central review will be documented in the IRC charter finalised prior to the enrolment of the first subject.

The BOR will be derived as defined in [Appendix 1 \(1\)](#).

Below is the **definition of the estimand** used for the primary efficacy endpoint :

Treatment : Cabozantinib

Population : Subjects with unresectable, locally, advanced or metastatic RCC with a clear-cell component who progressed after prior CPI therapy with ipilimumab and nivolumab in combination (Cohort A).

Endpoint : ORR defined as the proportion of PR and CR at any timepoint during treatment period (i.e. up to 30 days after the discontinuation of Cabozantinib) as determined by independent central review per RECIST1.1.

Intercurrent events :

- Study discontinuation without response (i.e. without PR or CR) during the treatment period (composite strategy)

Subjects withdrawn from the study without response during the treatment period or subjects without any post-baseline tumour assessment are non-responders.

- Treatment discontinuation prior to RECIST 1.1 progression (treatment policy strategy)

The efficacy assessment at any timepoint prior to RECIST 1.1 progression is used regardless of whether the Cabozantinib is discontinued.

- Subjects not treated (while on treatment strategy)

Subjects will not be included in the primary efficacy analysis.

- Subjects receiving non-protocol anti-cancer treatment (while on treatment strategy)

Assessment of the response during the treatment period, i.e. until the initiation of non-protocol anti-cancer treatment.

Population-level summary : ORR compared to the historical control value of 10%.

3.1.2 *Secondary efficacy endpoints*

The secondary efficacy endpoints are:

- (a) TTR defined as the time from start of study treatment to the date of first evidence of response (PR or CR as determined by independent central review per RECIST 1.1) (see [Appendix 1 \(2\)](#), for the derivation and censoring rules).
- (b) DOR defined as the time from first documented response (PR or CR as determined by independent central review per RECIST 1.1) to either disease progression (as determined by independent central review per RECIST 1.1) or death due to any cause. Censoring rules will be similar to those applied for progression-free survival (PFS) (see [Appendix 1 \(3\)](#)).

SAP Final: Version 6.0: 17 August 2023

- (c) DCR defined as the proportion of subjects with a BOR of a PR, CR or SD as determined by independent central review per RECIST 1.1
- (d) PFS defined as the time from start of study treatment to either disease progression (as determined by independent central review per RECIST 1.1) or death due to any cause, whichever occurs first (see [Appendix 1 \(4\)](#)).
- (e) ORR in cohort B defined as the proportion of subjects with a BOR of a PR or CR at any timepoint as determined by independent central review per RECIST 1.1
- (f) OS defined as the time from the start of treatment until death due to any cause (see [Appendix 1 \(5\)](#)).
- (g) ORR, TTR, DOR, DCR and PFS according to local Investigator's review per RECIST 1.1 and defined as for the independent central review,
- (h) Change in disease-related symptoms as assessed by the FKSI-DRS questionnaire.

The endpoints of ORR, TTR, DOR, DCR and PFS will be evaluated by tumour assessments (see [Section 1.3.2.1](#)). The OS will be assessed as described in [Section 1.3.2.1](#).

All these secondary endpoints will be presented in each cohort separately. In addition, ORR and PFS according to local Investigator's review per RECIST 1.1 as well as OS will be presented in the overall population (cohort A + cohort B).

Below is the **definition of the estimand** used for the secondary efficacy endpoint of duration of response:

Treatment : Cabozantinib

Population : Subjects with unresectable, locally, advanced or metastatic RCC with a clear-cell component who progressed after prior CPI therapy with ipilimumab and nivolumab in combination (Cohort A) with a PR or CR at any timepoint during the treatment period.

Endpoint : DOR defined as the time from first documented response (PR or CR as determined by independent central review per RECIST 1.1) to either disease progression (as determined by independent central review per RECIST 1.1) or death due to any cause, whichever occurs first.

Intercurrent events :

- Two or more missing scheduled tumour assessment prior to RECIST 1.1 progression (while on treatment strategy)

Subjects will be censored at the date of the last tumour assessment prior to the missing assessment.

- Subjects not treated (while on treatment strategy)

Subjects will not be included in the efficacy analysis.

- Subjects receiving non-protocol anti-cancer treatment prior to RECIST 1.1 progression (while on treatment strategy)

Subjects will be censored at the date of the last tumour assessment prior to the initiation of non-protocol anti-cancer treatment.

SAP Final: Version 6.0: 17 August 2023

- Treatment discontinuation prior to RECIST 1.1 progression (treatment policy strategy)

Subjects will be censored at the date of the last tumour assessment.

- Treatment discontinuation without any post-baseline tumour assessment (treatment policy strategy) after the first response to treatment

Subjects will be censored at the time of first documented response.

Population-level summary : median of DOR 2-sided 95% with CI.

3.1.3 *Safety endpoints*

Safety endpoints are adverse events, clinical laboratory test results, vital signs measurements, ECG and physical examination results, and use of concomitant medication.

Summaries of AEs and SAEs will be tabulated by cohort and overall, according to system organ class (SOC) and preferred term (PT) by overall incidence, worst reported severity, and relationship to study treatment. Selected laboratory test results will be summarised by cohort to evaluate worst post-Baseline Common Terminology Criteria for Adverse Events (CTCAE) grade, as well as shifts or changes from Baseline.

3.1.4 *Multiplicity*

No multiple testing will be performed in this study as no statistical testing will be carried out at the interim analysis for efficacy endpoints.

3.1.5 *Significance testing and estimation*

ORR (primary endpoint) will be tested at the final analysis as described in Section 3.2.1.1 using the one-sided significance level (alpha) of 0.025. No statistical testing will be carried out at the interim analysis for efficacy endpoints.

3.2 *Analysis methods*

3.2.1 *Efficacy*

Analysis based on the primary efficacy endpoint will be performed on the efficacy population in cohort A. Analyses based on the secondary efficacy endpoints will be performed on the efficacy population as defined in Section 2.1.1 and will be presented in each cohort separately. In addition, ORR and PFS according to local Investigator's review per RECIST 1.1 as well as OS will be presented in the overall population (cohort A + cohort B).

Sensitivity efficacy analyses will be based on PP population as defined in Sections 2.1.3 and 2.3. Efficacy analyses in the PP population will be presented if there is a difference greater than 15% between efficacy population and PP population. The difference will be checked for each cohort separately. In case the difference is greater than 15% for one cohort only, only this cohort will be presented in both efficacy population and PP population.

Additional supportive analysis of PFS, Kaplan-Meier and Waterfall plots will be performed only on efficacy population.

Subject data listings (Listings 16.2.6.1 to 16.2.6.8) will be based on Efficacy Population.

SAP Final: Version 6.0: 17 August 2023

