### 5.2.3 *Procedures After Study Treatment*

Subjects who discontinue study treatment with cabozantinib will be invited to enter the Post-treatment Follow-up period. All necessary assessments performed after treatment are indicated in [Table 2](#).

For subjects who have discontinued cabozantinib treatment before radiographic disease progression and who have not withdrawn consent, tumour assessment should be performed until radiographic progression confirmed by the Investigator.

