**Intercurrent events:**

- Two or more missing scheduled tumour assessment prior to RECIST 1.1. progression (while on treatment strategy)

Subjects will be censored at the date of the last tumour assessment prior to the missing assessment.

- Subjects not treated (while on treatment strategy)

Subjects will not be included in the efficacy analysis.

- Subjects receiving non-protocol anti-cancer treatment prior to RECIST 1.1 progression (while on treatment strategy)

Subjects will be censored at the date of the last tumour assessment prior to the initiation of non-protocol anti-cancer treatment.

- Treatment discontinuation prior to RECIST 1.1. progression (treatment policy strategy)

Subjects will be censored at the date of the last tumour assessment.

- Treatment discontinuation without any post-baseline tumour assessment (treatment policy strategy) after the first response to treatment

Subjects will be censored at the time of first documented response.

**Population-level summary:** median of DOR 2-sided 95% with CI.

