In case of response and a partial initial response date, missing day will be imputed by the last day of the month. This will be the most conservative approach considering the latest date for the response. It will be imputed by the first study drug intake in case the first study drug intake is earlier than the imputed date.

In case of censoring and a partial last tumour assessment date, missing day will be imputed by the first day of the month. It will be imputed by the first study drug intake in case the first intake is later than the imputed date. The censoring may occur earlier than the exact date.

(3) Duration of response (DOR)

DOR is defined as the time from first documented response (PR or CR) to either disease progression or death due to any cause, whichever occurs first. DOR will be analysed for responding subjects only. For responding subjects (i.e. subjects with a PR or CR) who are not known to be dead or progressed at the time of data cut-off for DOR analysis, the DOR will be censored at the last tumour assessment and considering the censoring rules defined in the table below.

| Event | Decision | Date of event or censoring |
|---|--------------|---|
| Progressive disease with no more than one missing scheduled tumor assessment before the event and without NPACT before the event. | Not censored | Date of first progressive disease |
| Death with no more than one missing scheduled tumor assessment before the event and without NPACT before the event. | Not censored | Date of death |
| PD or death with two or more missing scheduled tumor assessments before the event | Censored | Date of the last tumor assessment prior to the missing assessment. |
| PD or death with NPACT after the start of cabozantinib and before the event | Censored | Date of the last tumor assessment prior to the date of initiation of NPACT. |
| No event (no PD, no death) with at least one radiological assessment after the first response to treatment. | Censored | Date of last radiological assessment |

SAP Final: Version 6.0: 17 August 2023

| | | |
|---|----------|-------------------------------------|
| No event (no PD, no death) without any radiological assessment after the first response to treatment. | Censored | Date of first response to treatment |
|---|----------|-------------------------------------|

DOT will be calculated as:

DOT(months) = round ((progression date or death date or date of last tumour assessment – date of initial response+1) / (30.4375),0.01)

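### The DOR estimand labels stopping cabozantinib before progression as treatment policy, yet censors those responders without condition, against SAP Appendix 1 (3), which counts their later progression or death

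*SAP*

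**What the plan says.** The DOR estimand appears in protocol 11.4.3.2 and again, almost word for word, in SAP 3.1.2. Two of its intercurrent events concern stopping drug.

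- Stopping before progression: the SAP has "Treatment discontinuation prior to RECIST 1.1 progression (treatment policy strategy" and the protocol has "Treatment discontinuation prior to RECIST 1.1. progression (treatment policy strategy". The handling that follows is "Subjects will be censored at the date of the last tumour assessment".
- Stopping with no scan after the first response, also labelled treatment policy: "Subjects will be censored at the time of first documented response".

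Neither bullet is limited to subjects without progression or death.

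SAP 3.1.2 (b) says that DOR censoring resembles that for PFS and points to Appendix 1 (3). That table has no row for stopping drug. Two rows are marked as not censored: "Progressive disease with no more than one missing scheduled tumor assessment before the event and without NPACT before the event" and "Death with no more than one missing scheduled tumor assessment before the event and without NPACT before the event". Censoring at the last scan is reserved for "No event (no PD, no death) with at least one radiological assessment after the first response to treatment", and censoring at the response date for event-free subjects with no later scan.

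Protocol 5.2.3 says that, for subjects who stop before radiographic progression and have not withdrawn consent, "tumour assessment should be performed until radiographic progression confirmed by the Investigator".

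**The concern.** A treatment-policy strategy means that the intercurrent event is ignored and outcomes after it still count. Censoring everyone who stops drug does the opposite. The same patient can therefore be an event under Appendix 1 (3) and censored under the estimand, and a programmer cannot follow both.

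The rest of the plan sides with Appendix 1. The primary ORR estimand (SAP 3.1.1) uses assessments before progression whether or not cabozantinib has been stopped. The general PFS rules in protocol 11.4.3.4 do not censor for stopping. Such censoring appears only as an extra rule in the third supportive PFS analysis in SAP 3.2.1.2. Scanning after stopping makes the later events observable.

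DOR is the measure of whether the responses counted in the primary endpoint last, and it is the only secondary endpoint given an estimand. SAP 3.2.1.2 confines its supportive censoring analyses to PFS, so no planned output would show the effect of choosing one DOR rule over the other.

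**Working it through.** **1. The plan's own figure.** The documents state no DOR figure. The design figure they do give reproduces: exact binomial, n = 68, null 10%, one-sided 0.025. The rule is to reject at 13 or more responses, with alpha 0.0163 and power 0.816 at 23%. Inflation: 68/(1 − 0.07) = 73.1, rounded up to 74. The sample size is not at issue.

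**2. Responders concerned.** 68 × 0.23 = 15.6, about 16. The documents give no rate of stopping before progression. Assuming 20% to 30%: 16 × 0.20 = 3.2 and 16 × 0.30 = 4.8, so about 3 to 5 responders.

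**3. Two patients under each rule.** DOR in months = (end date − response date + 1)/30.4375, from Appendix 1 (3). Scans are every 12 weeks. Both patients respond at Week 12 and stop drug at Week 14, with no NPACT and no missed scheduled scan.

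| Patient | Appendix 1 (3) | Estimand, literal | Estimand, last scan before stopping |
|---|---|---|---|
| Progression at Week 24 scan | Event, 85/30.4375 = 2.79 | Censored, 2.79 | Censored, 1/30.4375 = 0.03 |
| Death at Week 20, no scan since response | Event, 57/30.4375 = 1.87 | Censored, 0.03 | Censored, 0.03 |

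**4. Effect on the median.** This was simulated with 40,000 responders per scenario. All of the following are assumptions, because the documents give none of them:

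- exponential DOR with an on-treatment median of 10 months;
- a 20% or 30% chance of stopping before the event (16% and 25% within the simulated follow-up);
- a hazard ratio (HR) after versus before stopping of 0.67 to 3;
- 10% of events being deaths;
- data cut-off 9 to 30 months after response.

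NPACT is left out because both rules censor it. Kaplan-Meier medians in months, continuous time:

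| Stopping | HR after stopping | Appendix 1 (3) | Last scan before stopping | Literal |
|---|---|---|---|---|
| 20% | 0.67 | 10.4 | 10.1 | 11.2 |
| 20% | 1 | 9.9 | 9.9 | 11.0 |
| 20% | 2 | 9.3 | 9.9 | 10.7 |
| 20% | 3 | 9.1 | 10.0 | 10.6 |
| 30% | 0.67 | 10.5 | 9.9 | 11.9 |
| 30% | 1 | 9.9 | 9.9 | 11.8 |
| 30% | 2 | 9.1 | 10.0 | 11.3 |
| 30% | 3 | 8.5 | 10.0 | 11.0 |

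Against Appendix 1 (3), the literal reading adds 0.8 (11.2 − 10.4) to 2.5 months (11.0 − 8.5). The other reading shifts the median by −0.6 (9.9 − 10.5) to +1.5 months (10.0 − 8.5), with no shift at HR 1.

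**5. With 12-week scans.** Medians fall on the scan grid. Under Appendix 1 (3) and the pre-stopping reading they are mostly 11.0 months. Under the literal reading they are 11.0 to 11.4 at 20% stopping and 13.8 at 30%. A difference can thus be hidden in the median and still show in the 12-month rate: at 30% stopping and HR 2 it is 42% under Appendix 1 (3), 45% under the pre-stopping reading and 51% under the literal one.

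**The case against.** The best defence is that a condition was left out. The two bullets line up one for one with the two event-free rows of Appendix 1 (3): last scan if there is a later one, response date if not. The estimand's endpoint line counts progression or death from any cause. SAP 3.1.2 (b) sends the reader to Appendix 1. Where the SAP wants a cut at stopping, it says so explicitly, and only as a supportive PFS analysis. On the literal reading, a patient would be censored on the very scan that shows progression, which few programmers would choose.

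This is plausible and may well be the intent, but the text does not say it. In the same list, the missed-scan and NPACT bullets use the same sentence form, and there Appendix 1 (3) confirms that the censoring does override a later event. One form would have to be read in two opposite ways. If the condition was simply omitted, the same edit is needed.

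It is also fair that DOR is secondary and, under protocol 11.3, not formally tested.

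A reader might go further and infer that the estimand rule always overstates DOR. The documents do not support that. It is certain only on the literal wording. If censoring is at the last scan before stopping, overstatement requires a higher hazard after stopping, and no such hazard is given. Nor can the size be found by dividing the median by one minus the share who stop. The divisor depends on the share of events removed, which is smaller: at HR 1 the simulation implies 1 − 9.9/11.0 = 0.10 for 20% stopping and 1 − 9.9/11.8 = 0.16 for 30%.

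**Conclusion.** The point holds. The estimand text, in both documents, contradicts its own treatment-policy label, SAP 3.1.2 (b) and Appendix 1 (3). Followed as written, it gives a different DOR from the one Appendix 1 (3) defines.

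On the literal wording the reported DOR is too long, by roughly 0.8 to 2.5 months in the median under the simulation's assumptions with 20–30% stopping. On the pre-stopping reading the direction is not determined. On the benign reading there is no difference.

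About 3 to 5 of some 16 responders are concerned if 20–30% stop before progression. Those who start NPACT first, or who miss two or more scans before the event, are censored under both texts. The responder count uses the design assumptions; SAP section 5 notes that cohort A enrolled beyond its target. The primary ORR test and its conclusion do not depend on this.

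**What to change.** In protocol 11.4.3.2 and SAP 3.1.2, keep the treatment-policy label and replace the text under both discontinuation bullets with:

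> Discontinuation of cabozantinib is ignored: progression or death after discontinuation counts as a DOR event on its own date, subject to the NPACT and missed-assessment censoring rules above. Subjects with no PD or death by data cut-off, and not otherwise censored, are censored at their last tumour assessment, or at the first documented response if there is no later assessment.

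This matches Appendix 1 (3). The reference to the NPACT and missed-assessment rules is essential: without it, a responder who stops, starts NPACT and then progresses would be an event under the new sentence and censored under the existing rules.

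The cost is a wording change, with no new data and no change to Appendix 1. The reported median DOR may be somewhat shorter than under the literal estimand rule. If DOR outputs already exist, the report should state which rule was programmed.
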